- Aim 1b: Participants will receive a 7-day supplement of L-citrulline or placebo before each study visit, with a washout period of 7 days between visits. The activity of the eNOS converts L-arginine into NO and L-citrulline, which is normally recycled back into L-arginine⁵⁷. Unlike L-arginine, oral ingestion of L-citrulline is not catabolized in the gut, nor is it extracted from systemic circulation through hepatic first-pass metabolism. Thus, ingested L-citrulline becomes available in large quantities in the plasma for enzymatic conversion into L-arginine⁵⁵, thereby increasing endothelium-dependent NO bioavailability. The 7-day L-citrulline administration is effective to increase L-arginine plasma levels and NO signaling in a dose-dependent manner⁵⁵, while a single administration has failed to do so⁵⁸.
- Aim 1c: At the beginning of each visit, participants will ingest a liquid mixture prepared by Investigational Drug Services at UMMC containing Sildenafil or placebo. Sildenafil inhibits phosphodiesterase 5 (PDE5), an enzyme that degrades cGMP in the vascular smooth muscle cells inactivating the NO-mediated signal; thus, Sildenafil will prolong the availability of cGMP, enhancing the NO-mediated intracellular cascade.

For Aim 2, a double-blind, randomized, placebo-controlled crossover design will be used to examine the role of ET-1 on the vascular function of young Black and White individuals. Two visits will be performed, with a minimum of 7 days between them. At the beginning of each visit, participants will ingest a liquid mixture prepared by Investigational Drug Services at UMMC containing Bosentan or placebo. Bosentan blocks ET_A and ET_B receptors, leading to a reduction in vasoconstrictor tone and a greater magnitude of vasodilator responses.

EXPERIMENTAL VISITS: Figure 4 displays the design of the experimental visits. Participants will abstain from alcohol consumption, caffeine, and exercise for 24 h before all study visits, and will come after fasting overnight. Experiments will be conducted in a room with temperature tightly controlled at $20\text{--}21^{\circ}\text{C}$ to minimize the influence of skin blood flow on the Doppler ultrasound measures. Women will participate in the study during the early follicular phase of the ovarian cycle to minimize variability in physiological responses across the menstrual cycle.

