For Aim 1a, upon arriving at the laboratory, subjects will ingest 140 mL of a beetroot juice containing either a high (~ 12.8 mmol) or a low concentration (~ 0.0055 mmol) of nitrates (James White Drinks, Suffolk, UK)^{59,60}, in random order over two consecutive visits. Ninety minutes will be allowed after beverage ingestion to start

instrumentation to ensure that data collection occurs in the period of peak nitrate plasma concentration (i.e., 120 min)⁶⁰.

For Aim 1b, participants will receive pills containing 3 g of L-citrulline (Superior Labs, Park City, UT) or placebo, to be taken twice daily for 7 days each, before each study visit. The washout period will be 7 days. On the day of the study visit, subjects will ingest the last supplement or placebo pill upon arriving at the laboratory. Sixty minutes will be allowed before start instrumentation to ensure that data collection occurs in the period of peak L-arginine plasma concentration (i.e., 90 min)⁵⁵.

For Aim 1c, upon arriving at the laboratory, subjects will ingest a liquid mixture containing the PDE5 inhibitor Sildenafil (100 mg)⁶¹, or placebo in random order. Thirty minutes will be allowed after drug ingestion to start instrumentation to ensure that data collection occurs in the period of peak plasma concentration of Sildenafil (i.e., 60 min)⁶².

For Aim 2, upon arriving at the laboratory, subjects will ingest a liquid mixture containing the non-selective ET_A and ET_B receptors antagonist Bosentan (125 mg)³³, or placebo, in random order over two consecutive visits. Ninety minutes will be allowed after drug ingestion to start instrumentation to ensure that data collection occurs in the period of peak plasma concentration of the drug (i.e., 120 min)⁶³.

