Study visits will be scheduled in pairs according to each specific aim of the project. In other words, each intervention and its respective placebo will be scheduled for consecutive visits. Participants will receive gift cards after completing each pair of visits. Furthermore, participants will learn more about the development of physiological studies in humans. Particularly for UMMC students, this experience may contribute for deciding to pursue a career in human physiology research.

	Fall 2020	Spring 2021	Fall 2021	Spring 2022	Fall 2022	Spring 2023	Fall 2023
Studies – Specific Aim 1a							
Studies – Specific Aim 1b							
Studies – Specific Aim 1c							
Studies – Specific Aim 2							
Abstract submissions							
Manuscript submissions							
IRB – Initial submission							
IRB – Amendments and new protocols							
Funding – COBRE Pilot Grant Program submission							
Funding – AHA Career Development Award submissions							
Funding – NIH Research Project Grant (R01) submissions							

PROTECTION OF HUMAN SUBJECTS

- Risks to Human Subjects

- a. Human Subjects Involvement, Characteristics, and Design

Cardiovascular diseases (CVD) are disproportionately more prevalent in Black (i.e., African American) men and women than in other racial groups in the U.S., which has been associated with deleterious alterations in vascular function starting early in life in Black individuals. Our research is designed to examine the impairments in vascular function in young Black individuals compared with White individuals, understand the contributions of nitric oxide (NO; Aim 1) and endothelin-1 (ET-1; Aim 2) driving these racial differences, generate evidence on potential interventions to improve vascular function and support future clinical practices to prevent CVD in the Black population.

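### Aim 1b's 7-day course and flat 7-day washout put paired visits about 14 days apart, so a woman with a cycle of about 21 days or more cannot be early follicular at both, as the plan requires

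*Combined protocol and SAP*

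**What the plan says.** All of this is in the Combined protocol and SAP, mostly under Research Strategy, Approach.

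- **Phase rule.** The opening paragraph of Experimental Visits, which covers every aim, says: "Women will participate in the study during the early follicular phase of the ovarian cycle". The reason given is "to minimize variability in physiological responses across the menstrual cycle". Aim 1b is not exempted, and no range of cycle days is given.
- **Aim 1b course.** Pills are "to be taken twice daily for 7 days each, before each study visit". On the visit day, "subjects will ingest the last supplement or placebo pill upon arriving at the laboratory".
- **Aim 1b washout.** Study Design says "with a washout period of 7 days between visits", and Experimental Visits repeats: "The washout period will be 7 days". Neither place calls this a minimum.
- **Aim 2, for contrast.** Study Design says: "Two visits will be performed, with a minimum of 7 days between them". The separate bosentan Research Protocol (Study Design row) allows 1 to 12 weeks between its two treatment visits.
- **Pairing.** The Recruitment and Retention Plan says "each intervention and its respective placebo will be scheduled for consecutive visits".
- **Women planned.** Inclusion of Women and Minorities gives 15 Black and 15 White women among 60 participants.

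**The concern.** Aim 1b is the only aim with a multi-day course before each visit, and its washout is a single fixed number. The phase rule ties each woman's visits to a recurring part of her cycle. If the fixed spacing is shorter than the time until that part recurs, staff cannot follow both rules and nothing says which takes priority.

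If the phase rule gives way, the two visits being compared within a woman fall in different cycle phases. That is the source of variability the plan set out to remove. It would enter the within-person drug contrast and the race-by-drug interaction, which carry the Aim 1b hypothesis, and it would affect every participant in the planned sub-analysis of women.

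**Working it through.** The plan gives no figure to reproduce; this is calendar arithmetic.

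**Inputs from the documents:** course 7 days, last pill on the visit day, washout 7 days, 30 women, two Aim 1b visits each.

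**Assumptions, because the documents are silent:** early follicular is cycle days 1 to w, with w = 5 or 7; cycle length L is 21 to 35 days.

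**Step 1: gap between visits.** Call visit 1 day 0. Days 1-7 are pill-free and days 8-14 are the second course, with visit 2 on day 14. Gap = 7 + 7 = 14 days. Two other readings were checked:
- Seven full days of pills before a visit-day pill gives a gap of 15.
- Seven days from visit to visit, taken literally, gives a gap of 7 and leaves no pill-free time at all.

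**Step 2: cycle day of visit 2.** If visit 1 is on cycle day d, visit 2 is on day ((d − 1 + gap) mod L) + 1. With a gap of 14 and d = 1-7, visit 2 is 14 days further on: days 15-21 for any cycle of 21 days or more.

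**Step 3: can both visits be in the window?** The best case is visit 1 on day w and visit 2 on day 1 of the next cycle. This needs L ≤ gap + w − 1.

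| Gap (days) | Longest L, w = 5 | Longest L, w = 7 | Matches for L = 21-35, w = 5 | Matches for L = 21-35, w = 7 |
|---|---|---|---|---|
| 7 | 11 | 13 | 0 of 75 | 0 of 105 |
| 14 | 18 | 20 | 0 of 75 | 0 of 105 |
| 15 | 19 | 21 | 0 of 75 | 1 of 105 |

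The denominators are 15 cycle lengths times w starting days. The single match is a 21-day cycle going from day 7 to day 1. For a 28-day cycle the window would have to reach day 15 before a 14-day gap could fit.

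**Step 4: washouts that satisfy both rules.** Compliant gaps run from L − (w − 1) to L + (w − 1), and washout = gap − 7.

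| L (days) | Washout, w = 7 | Washout, w = 5 | Same cycle day (L − 7) |
|---|---|---|---|
| 21 | 8-20 | 10-18 | 14 |
| 28 | 15-27 | 17-25 | 21 |
| 35 | 22-34 | 24-32 | 28 |

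The stated 7 days is below every one of these ranges.

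**Step 5: visits affected if the washout is kept.** 30 women × 2 = 60 woman-visits, with at most one in phase per woman, so at most 30. At the target before allowance for data loss (11 doubled to 22 per racial group, half of them women, so 22 women), at most 22 of 44.

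The documents give no cycle-phase effect and no within-person SD, so the loss of precision cannot be computed.

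**The case against.** The strongest reply is that a washout says how long carry-over needs to clear. No upper limit is justified anywhere, so a sensible reader would take 7 days as a floor and wait for the next suitable cycle. The bosentan Research Protocol points that way: it allows up to 12 weeks and asks women about their most recent period at each visit. Interval wording is loose throughout (Aims 1a and 1c state none). Protections Against Risk says only a portion of the procedures has ethics approval and that amendments will follow, so scheduling detail could come later.

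Much of this stands. If 7 days is a minimum, both rules can be met, and the count of out-of-phase visits applies only if the phase rule is the one that yields. But the text states a flat 7 days twice for Aim 1b and writes a minimum only for Aim 2. The bosentan protocol indicates practice for another aim; it does not settle this one.

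A reader might infer that half of women's Aim 1b visits will be out of phase, or that the L-citrulline effect will be biased. The documents support neither. They do not say which rule would give way, and the order of drug and placebo is randomised. If visit 1 were always in phase and visit 2 always 14 days later, the average shift would be a period effect in women. A period-by-sex term could remove that average, leaving only the variation between women; the stated ANOVA lists drug, group and their interaction, with no period term. Finally, 30 women is an upper limit, since participants may decline an intervention.

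**Conclusion.** The point holds for Aim 1b as written. Two stated rules cannot both be followed by a woman with a cycle of about 21 days or more (22 or more on the 15-day reading with a days 1-7 window). This rests on the assumed window of days 1-7 or shorter and on reading the washout as exactly 7 days. It is a conflict between rules, not just an omitted detail.

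The consequence depends on how staff resolve it. Keeping the washout leaves at most one in-phase visit per woman and costs precision of unknown size; extending it costs only calendar time. Men are unaffected, and Aim 2's open-ended interval does not share the problem. Severity is minor to moderate.

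**What to change.** Replace the Aim 1b washout statement with wording such as:

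> At least 7 days; for women, the second 7-day course is timed so that visit 2 falls in the early follicular phase of a later cycle.

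For a 28-day cycle this means about 21 days' washout. In addition:

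- **Define the window in days**, and start each course from the predicted date of menses so that it ends inside the window. A 7-day course ending on planned cycle day t starts 7 − t days before day 1, and menses k days late puts the visit on day t − k. For days 1-5, plan day 3: start 4 days before, with a tolerance of 2 days either way. For days 1-7, plan day 4: start 3 days before, with a tolerance of 3 days.
- **Keep the course at 7 days with the last pill on the visit day.** If menses timing puts the visit outside the window, repeat the assigned course in the next cycle. Extending the pills until menses begins would break both the 7-day course and the rule that the last pill is taken on arrival.

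**Cost.** Two or three sentences, which can go into the Aim 1b amendment. Women's pairs take 28 − 14 = 14 days longer for a 28-day cycle (7 to 21 days longer for cycles of 21 to 35 days). Spare pills are needed and an occasional visit will be rescheduled. Predicting menses is no new burden for visit 1, because the present text already requires a 7-day course that ends in the early follicular phase.

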Figure 4. Protocol of the experimental visits. Visits will be identical except for the oral drug or supplement administration before any procedure.

STATISTICAL ANALYSES: Sample size estimation (statulator.com) is 11 individuals per group, based on the femoral artery blood flow response to knee extension exercise from our preliminary data (see below), using Student's *t*-test for independent samples, and considering a two-tailed alpha of 0.05, and power of 0.8 as parameters. This estimated sample size is adequate relative to our previous investigations^{10,11}. Due to potential influence of sex and race on vascular function⁶⁹, we will duplicate the estimated sample size to recruit an equal number of men and women. To account for incompleteness and exclusion of data during analyses, additional participants will be recruited, leading to an estimate of 30 individuals enrolled in each racial group. We will use a mixed-model ANOVA to compare vascular responses according to the effects of drug administration (Placebo vs. Drug), group (Black vs. White), and interaction. Subjects' characteristics will be compared using Student's *t*-test for independent samples and, in case of significant differences, such characteristics will be used as covariates in the ANOVA. Additionally, while men and women will be primarily grouped according to race, the large and balanced sample size will allow for sub-analyses comparing the effects of race on vascular responses separately in men and women.

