PRELIMINARY STUDY: We recently compared common femoral artery blood flow (FABF, Doppler ultrasound) between White (*n* = 4) and Black (*n* = 8) healthy young men during knee extension exercise at 10 W, 20 W, and 30 W. Each exercise trial lasted for 3 min with a minimum rest interval of 5 min. Knee extension cadence was 50 repetitions per min dictated by a metronome and by real-time visual feedback. The participants performed an incremental knee extension exercise test to determine their maximal workload on a separate visit. The groups were of similar age (White men: 21 ± 2 years vs. Black men: 21 ± 1 years; *P* = 0.905), body mass index (White men: 21.3 ± 2.1 kg/m² vs. Black men: 23.2 ± 3.4 kg/m²; *P* = 0.319), and achieved similar peak workloads in the maximal exercise test (Whites: 48 ± 15 W vs. Blacks: 52 ± 9 W; *P* = 0.542). FABF response to exercise was lower in Black men compared with White men across all workloads (Group *P* = 0.038; Figure 5). In this preliminary study, we have been able to demonstrate the necessary skills to establish the proposed comprehensive assessment of racial differences in vascular function and generated data to support our hypothesis of reduced leg blood flow response to knee extension exercise in Black men compared with White men.

[figure not shown]

Figure 5. Individual and mean group changes in femoral artery blood flow from rest to knee extension exercise at 10W, 20W, and 30W in White men (light grey bars, white circles) and Black men (dark grey bars, black circles).

EXPECTED RESULTS AND FUTURE PLANS TO SECURE EXTRAMURAL FUNDING

Black individuals manifest impaired vascular responses compared with White individuals. We postulate that this is due, at least in part, to a low NO dilator signaling and a high ET-1 constrictor signaling. Accordingly, we anticipate that:

- Increases in conductance and arterial diameter in response to the experimental procedures (flow-mediated dilation, passive leg movement, rhythmic handgrip, and knee extension) will be lower in Black than in White individuals in the placebo visits.
- Increase in NO bioavailability with beetroot juice and L-citrulline, and the increase in cGMP with Sildenafil will augment the dilator signal and increase vascular responses in Black individuals, attenuating the impairment in comparison with White individuals.

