Purpose	
To begin to elucidate the alterations in vascular function in Black individuals, we chose to target ET-1, a peptide produced by the vascular endothelium that mediates vasoconstriction by binding ET_A and ET_B receptors on smooth muscle^{14,15}. ET-1 seems to play a prominent role in the pathophysiology of hypertension specifically in Black patients^{16,17}. Also, it is suggested that ET-1 may be associated with impaired vascular control of blood pressure in young normotensive Black men¹⁸. Vascular responsiveness to ET-1 is also upregulated in adults exposed to insults during their fetal life (e.g., poor maternal nutrition, chronic stress, no prenatal care), psychological stressors during childhood (e.g., physical and emotional abuse, household dysfunction), and high ethnic discrimination¹⁹⁻²⁴—all of which are more prevalent among Black than White individuals, possibly contributing to racial disparities in vascular function²⁵⁻²⁸. We hypothesize that Black individuals have reduced vasodilator responses as a consequence of a greater vasoconstrictor tone mediated by ET-1. Therefore, we hypothesize that the antagonism of ET_A and ET_B receptors will reduce the vasoconstrictor tone and augment the vasodilator responses in Black but not in White individuals.

Specific Aim	
We will examine the role of ET-1 on brachial and popliteal artery flow-mediated dilation, reactive hyperemia, and blood flow responses to passive leg movement, rhythmic handgrip exercise, and rhythmic knee extension exercise between Black and White individuals. Using an acute oral administration of Bosentan, we will antagonize ET_A and ET_B receptors to reduce the vasoconstrictor tone mediated by ET-1 and, consequently, allow for greater flow-mediated dilation, reactive hyperemia, and blood flow responses to passive leg movement, handgrip, and knee extension. We anticipate that this effect of Bosentan will be more prominent in Black individuals than in White individuals. In a separate visit, the participants will receive a Placebo to serve as a control. We will also examine prenatal and at-birth medical records, and apply questionnaires of adverse childhood experiences and perceived discrimination to assess whether these early-life risk factors are associated with racial disparities in vasodilation between Black and White individuals.

Study Period	
3 years Anticipated start date: 09/01/2020 Anticipated end date: 09/01/2023

Data Generation Period	N/A

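### Covariates are chosen by between-race t-tests from an unlisted set, and the form of the covariate term is not stated, so the drug-by-race test may go unadjusted

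*Combined protocol and SAP*

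**What the plan says.** Under Statistical Analyses in the Research Strategy, and again under Statistical Design and Power, the main analysis is a mixed-model ANOVA with the "effects of drug administration (Placebo vs. Drug), group (Black vs. White), and interaction". Subject characteristics are compared between races by independent t-test, and "in case of significant differences, such characteristics will be used as covariates in the ANOVA".

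Three things are left open. The characteristics are not listed. No alpha is given for the comparisons. The text does not say whether a covariate enters as a main effect only or is also crossed with drug.

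The endothelin-1 Research Protocol has its own Statistical Methodology entry for Bosentan. It specifies two-way and three-way mixed-model ANOVAs and names no covariates. Aim 2 is therefore covered by two plans that differ on adjustment.

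**The concern.** Drug order is randomised; race is not. Any comparison between Black and White participants is observational, and characteristics that differ by race can confound it. A rule that adjusts only when a t-test is significant ties adjustment to the power of that t-test, which is modest at these sizes.

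The aims also predict a drug benefit in Black but not in White participants. That is a claim about the drug-by-group interaction. A characteristic that differs by race and also changes the response to drug will bias that interaction. Each intervention is given as a fixed amount, so body size is a plausible example. Adjustment helps here only if the covariate is allowed to act on the drug effect, and the plan does not say that it is.

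**Working it through.** **Inputs.** The Research Strategy gives 11 per group ("Sample size estimation (statulator.com) is 11 individuals per group"). It then says "we will duplicate the estimated sample size to recruit an equal number of men and women", which makes 22 per race, "leading to an estimate of 30 individuals enrolled in each racial group". The endothelin-1 protocol calculates 21 per group and enrols 25. The sample size calculation uses a two-sided alpha of 0.05 ("considering a two-tailed alpha of 0.05, and power of 0.8 as parameters"); I assume the same level for the screen. The documents give no figure for the performance of the covariate rule, so there is none to reproduce, and the derivation of 11 per group does not bear on this point.

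**1. Preliminary BMI gap.** The Preliminary Study reports "White men: 21.3 ± 2.1 kg/m² vs. Black men: 23.2 ± 3.4 kg/m²", P = 0.319, with 4 White and 8 Black men.
- Pooled SD = √[(3 × 2.1² + 7 × 3.4²)/10] = √9.415 = 3.07.
- Standardised gap = 1.9/3.07 = 0.62.
- t = 0.62/√(1/4 + 1/8) = 1.01 on 10 df, P = 0.336. The range is 0.305 to 0.368 once rounding of the summaries is allowed for, which is consistent with the stated P.
- The 95% interval for the standardised gap is about −0.63 to 1.83.

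The 0.62 is therefore only an illustration.

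**2. How often the screen misses a true imbalance.** Two-sided t-test, df = 2n − 2, noncentrality d√(n/2). Example: d = 0.5 and n = 30 give 0.5 × √15 = 1.94; power is 48%, so 52% are missed.

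| n per group | missed, d = 0.3 | d = 0.5 | d = 0.62 | d = 0.8 |
|---|---|---|---|---|
| 21 | 84% | 65% | 50% | 28% |
| 22 | 84% | 63% | 48% | 26% |
| 25 | 82% | 59% | 43% | 21% |
| 30 | 79% | 52% | 34% | 14% |

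The observed gap must reach 0.61 SD (n = 22) or 0.52 SD (n = 30) to be selected. The screen also picks up noise. If k independent characteristics do not differ, at least one is selected with probability 1 − 0.95^k, which is 23% for k = 5 and 40% for k = 10. The documents do not give k.

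**3. What a main-effect covariate does to the interaction.** Write the response as: intercept + b·drug + c·race + e·(drug × race) + f·X + person effect + error, where X is a person-level covariate. With both visits observed, the drug-minus-placebo difference is b + e·race + error, because f·X and the person effect cancel. The estimate of e is the same with or without X. A covariate-by-drug term h·(X × drug) would remain in the difference as h·X.

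One simulated two-visit data set, 30 per group, confirms this:

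| model | drug × race (SE) | race term |
|---|---|---|
| no covariate | −0.1798 (0.2439) | −0.009 |
| covariate main effect | −0.1798 (0.2439) | −0.329 |
| plus covariate × drug | −0.364 (0.252) | −0.237 |

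With 10% of visits removed, the main-effect covariate moved the interaction slightly, from −0.287 to −0.265.

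**4. False positives in the interaction test.** Assumptions, not from the documents: the covariate differs by race by g SD, correlates r with the drug-minus-placebo difference within race, there is no other race difference in drug response, and pairs are complete. The apparent race difference in drug response is then r × g SD, and the noncentrality is r·g·√(n/2). Example: 0.4 × 0.62 × √12.5 = 0.248 × 3.54 = 0.88, which gives 13.8% rejection at nominal 5%.

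| n per group | g = 0.3, r = 0.2 to 0.4 | g = 0.62, r = 0.2 to 0.4 |
|---|---|---|
| 21 | 5.4% to 6.7% | 6.8% to 12.3% |
| 25 | 5.5% to 7.0% | 7.1% to 13.8% |
| 30 | 5.6% to 7.4% | 7.6% to 15.7% |

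Simulation at 25 per group agrees, with 14% to 15% at the upper corner. With the covariate-by-drug term included, the simulated rate is about 5% throughout.

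**The case against.** The strongest reply is that main-effect entry is inferred. The text says only that characteristics are used as covariates, and some repeated-measures routines cross covariates with the within-person factor by default. If that happens, the interaction test after the screen has a false-positive rate of about 5% to 6% in simulation. This is fair, and so the interaction point is conditional. But it leaves adjustment of the key test to a software default.

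A reader might infer more than the documents support, in three ways.

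- *That the planned covariates can never affect the drug-by-race test.* The cancellation is exact only for complete pairs and a main effect, and the plan itself expects incomplete data. A main-effect covariate also does useful work on the between-race comparison at the placebo visits, which the plan names as an expected result.
- *That the rule adjusts away mediators.* The endothelin-1 protocol describes early-life adversity and discrimination as "more prevalent among Black than White individuals, possibly contributing to racial disparities in vascular function". These measures appear only in that protocol, which names no covariates, and it gives them a separate question. Nothing lists them among the characteristics to be screened. The open list fails to exclude them; it does not include them.
- *That a 0.62 SD BMI gap is established.* It comes from 12 men and its interval includes zero.

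Design controls also limit confounding. Sex is balanced by race at 15 per cell. The Research Strategy restricts age to 18 to 40 years and BMI to at most 30 kg/m², and excludes disease, medication and tobacco. Handgrip and knee-extension loads are set relative to each person's maximum. These controls narrow the possible imbalance but do not remove it, and the endothelin-1 protocol admits BMI up to 35 kg/m².

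**Conclusion.** The concern holds in two parts.

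The first does not depend on how covariates enter the model: selecting them by significance test from an unlisted set is a poor rule when the groups are not randomised. It misses a true half-SD imbalance 52% to 65% of the time at 21 to 30 per group, assuming the screen is run at two-sided 0.05.

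The second is conditional. If covariates enter as main effects only, then with complete pairs the drug-by-group test is unadjusted. Its false-positive rate at 25 per group is then about 5.5% to 7% for a 0.3 SD gap and 7% to 14% (up to 15% in simulation) for a 0.62 SD gap, against about 5% with covariate × drug. Those rates rest on an assumed correlation of 0.2 to 0.4 between covariate and drug response; the upper end is the least favourable corner of that range, not an expected value.

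This should be fixed before analysis, but it does not invalidate the design.

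**What to change.** Delete the t-test screen. Name a short covariate set chosen on causal grounds from data already collected, for example age and BMI (or body mass), with sex as a design factor. Enter each covariate mean-centred, as a main effect and as covariate × drug, whatever its observed balance. Report the unadjusted result alongside. Put the same rule into the Statistical Methodology entry of the endothelin-1 protocol, so that Aim 2 has one plan.

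State that the early-life, ACE and SEE measures stay out of the primary model. Do the same for peak workload: it may itself reflect the impaired exercise blood flow under study, so adjusting for it could remove part of the effect sought. All of these can be used in explanatory or sensitivity analyses.

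The cost is a change of wording and a few degrees of freedom. Keeping the set short matters at 21 to 30 per group. No new measurements are needed.
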